BL** = If assessments are not completed at baseline visit, they may be completed at next research appointment (i.e., first MRI appointment)

I = Intervention - weekly (every 5 session) rating scales are assessed following standard PVAMC clinical neuromodulation treatment protocols

I^ = Assessment is given during the 12 weekly BCBT therapy visit

EP = 12th intervention therapy visit, 12 weeks (3 months) from start of intervention

F/U = 6-, 12-, and 24- month follow-up visits. Veterans will attend the follow-up visits per study involvement as described in *Section D4.1 Study Visits*.

F/U* = Measure is not administered in the absence of history of STBs

D4.2 MRI Visits and Cognitive Battery

All MRI visit activities (pre-intervention/post-intervention and for control participants) will involve the same procedures. Specifically, all will include self-reports, a brief battery of PhenX and NIH Toolbox cognitive test delivered via iPad, and an MRI scan. All visits will take place in a private consult room in PVAMC building 32 and the PVAMC MRI Suite.

MRI Visit 1 activities will occur as soon as scheduling allows after baseline visit, prior to the start of TMS+BCBT intervention, if applicable, and MRI Visit 2 will occur post-intervention, if applicable, as soon as scheduling allows following the final intervention appointment. Control participants will have the MRI visit as soon as scheduling allows following the baseline visit.

Cognitive testing data is collected with a laptop during some MRI scans. Images will be acquired on a Siemens (Erlangen, Germany) PRISMA 3T scanner and 64-channel head coil at the PVAMC MRI facility. All equipment used in the scanning room are MRI compatible. Participants will receive \$75 for completion of the MRI visit. Compensation will be prorated for participants who do not complete the MRI scan if an attempt to complete the MRI scan is made.

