Follow-up assessments will be conducted in-person or if necessary, by telephone 6, 12, and 24 months from the start of the intervention period. When assessments are conducted remotely, de-identified data may be collected by study staff at home due to remote connection issues (due to COVID-19). To reduce attrition, subjects will be paid \$50 in electronic funds transfer (EFT) or gift cards for completion of each follow-up appointment. Veterans participating in TMS+BCBT and neuroimaging will attend follow-up visits at 6, 12, and 24-months. Veterans only participating in TMS+BCBT will attend follow-up visits at 6- and 12-months. Veterans and matched controls participating only in the neuroimaging and cognitive battery will attend follow-ups at 6-, 12-, and 24-months.

D4.5.1 Blinded Assessment Administration: At the intervention endpoint visit, and 6-, 12-, and 24-month follow-up visits, assessments will be administered by study personnel who are blind to TMS condition (active vs. sham). For veterans who participate in the intervention component of the study, these assessments will not be administered by the study therapist or TMS provider even though they are also blind to the TMS condition. All study personnel will be blind to the study condition at baseline.

D5. Electronic Health Record (EHR) Data Extraction

Study staff will manually extract EHR data from participants' VA CPRS files. Extracted values will be entered into VA REDCap in anonymized format (by patients' study ID only). The initial data extraction will occur at baseline no later than one week of the participant's MRI Visit or beginning of intervention. Subsequent data extractions will take place six months, one year, and two years after starting intervention. At each time point (baseline,

+6months, +1 year, +2 years), data for the current month, and for each of the 12 prior months will be extracted.

D5.1 EHR predictor extraction:

Participants' CPRS files will be manually reviewed by the PI or by trained study staff. The following data types will be manually extracted from CPRS files: 1) Health services utilization; 2) pharmaceutical utilization; 3) changes in pharmaceutical utilization; 4) mental health diagnoses. Factors under consideration were selected based on prior demonstrations of machine learning applied to EHR ³⁹⁻⁴¹. Related information such as names of medications and medical conditions will also be extracted.

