We will conduct 1 interim analysis and assess our primary aim when we have enrolled 32 persons per treatment group (~50% enrollment). The analyst and investigators will be blinded to treatment assignment in the interim analysis. We will test our a priori hypotheses and suggest consideration of early stopping to the DSMB if either group shows an effect on the primary outcome using O'Brien-Fleming stopping bounds [45] (i.e., a significance level of 0.0054). We will retain a significance level of 0.049 for our primary hypothesis at project completion.

E2.2 Primary hypothesis

We hypothesize that compared to sham TMS+BCBT, Veterans receiving active TMS+BCBT will demonstrate superior improvements in suicidal ideation and fewer suicide attempts. Our primary outcome for this aim is a composite measure of suicide behavior based on occurrence of any of five types of suicidal behavior: death by suicide, suicide attempt, interrupted or aborted attempts, and suicide preparatory acts. This composite score is derived from the Columbia Suicide Severity Rating Scale (C-SSRS). The C-SSRS captures data on number of attempts, aborted attempts, and interrupted attempts. Number of suicide behaviors will be added across these categories to yield a total suicide events score. Death by suicide will be captured by review of medical records and death records. The main exposure variable of interest is the random treatment assignment. Our analytic approach will be an ANCOVA-type mixed effect regression model [72]. This means the outcome composite measure at follow-up time points (e.g., 3, 6, 12 months) will be regressed on baseline value of the outcome, design factors, and treatment assignment, dummy variables for time (baseline as reference) and interactions of treatment assignment and time dummies. Random intercepts and exchangeable error covariance structure will accommodate non-independence of observations owing to the repeated measures design.

The main effect of TMS as adjunctive to BCBT will be tested with the main effect of group assignment to the joint intervention condition. The time effect interactions of TMS assignment test hypotheses about the maintenance of gains at 3, 6 and 12 months. Our main hypothesis is that there is an immediate beneficial effect of TMS exposure. For our secondary outcome, (time to first suicide attempt over 12 months) we will use a Cox proportional hazards model analysis framework.

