E2.2.1 Statistical power and sample size for our primary outcome: With 65 persons per group, Lehr's equation [73] instructs that minimum detectable standardized mean difference effect size difference (d) between treatment groups at the baseline assessment is $\text{sqrt}(16/n)$, where n is the per-group sample size, or 0.50 standard deviation units, a medium effect size in Cohen's effect size taxonomy [74]. Given the ANCOVA design, we will be able to detect a smaller effect depending upon the magnitude of the pre-post correlation (r) of the suicidal behavior composite outcome $\{d = \text{sqrt}([16(1-r^2)]/n)\}$, which under the assumption of a moderate correlation (r = .2) the minimum detectable effect size is $d = .47$. These are medium or typical effect size magnitudes [75] and are likely to describe effects of minimal clinical significance or practical importance. Of note, these are also comparable with prior TMS studies [64,65] who described effect sizes of .5-.52, and more recent studies indicating larger (d=.9) effect sizes of TMS used with medications [76]. While we recognize these are effect sizes for depressive symptoms, in our pilot work we found reduction in depressive and suicide-related symptoms to be highly correlated. For our secondary outcome, we used simulations to determine the minimum detectable difference. If we assume that 21% of the sample will experience a suicide attempt over 12 months follow-up, if the cumulative risk of suicide attempt is 4.5% over 12 months in the TMS+BCBT group (hazard ratio = 0.19) we

will have 81.1% power to detect such an effect using a type-I error rate of 5% in a Cox proportional hazards model framework.

E2.3 Secondary hypotheses

For this aim we hypothesize, compared to sham TMS+BCBT, Veterans who receive active TMS+BCBT will have superior improvements in psychosocial functioning and fewer psychiatric hospitalizations/crisis visits during the follow-up period. The outcomes for this aim are a)

WHODAS score b) number of psychiatric hospitalizations/crisis visits c) reduced suicide ideation as measured by the C-SSRS. The analysis for the psychosocial functioning outcome, (a), and the suicidal ideation severity score from the C-SSRS, (c), will be a repeated measures ANCOVA, as with the primary hypothesis, using a generalized linear mixed effect model. For part (b), the outcome will be a count variable, for which we will use negative binomial regression.

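### The primary mixed model forces one variance on event counts at every visit, so visit-specific effects can get wrong standard errors; the doubled random intercept and exchangeable covariance are only redundant

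*Combined protocol and SAP*

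**What the plan says.** Section E2.2 defines the primary outcome as a count: "Number of suicide behaviors will be added across these categories to yield a total suicide events score". It describes an ANCOVA-type mixed effect regression in which "the outcome composite measure at follow-up time points (e.g., 3, 6, 12 months) will be regressed on baseline value of the outcome", with design factors, treatment, time dummies and treatment-by-time interactions. The covariance is set in one sentence: "Random intercepts and exchangeable error covariance structure will accommodate non-independence of observations owing to the repeated measures design".

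The treatment effect is tested through the group main effect, and section E2.2 adds: "The time effect interactions of TMS assignment test hypotheses about the maintenance of gains at 3, 6 and 12 months".

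The visit times come from elsewhere. The note to Table 2 has "EP = 12th intervention therapy visit, 12 weeks (3 months) from start of intervention", and D4.5 (Follow-Up Visits) places the later assessments "by telephone 6, 12, and 24 months from the start of the intervention period". The visits to 12 months are therefore 3, 3 and 6 months apart.

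On what is counted, E2.2 says only "The C-SSRS captures data on number of attempts, aborted attempts, and interrupted attempts". Nowhere is it stated whether each visit counts events since the previous visit, since the start of treatment, or over some other period.

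Section E2.3 says that the analysis of WHODAS and ideation severity "will be a repeated measures ANCOVA, as with the primary hypothesis, using a generalized linear mixed effect model".

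**The concern.** Two things look wrong, and they differ in weight.

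First, a random intercept with independent errors already implies an exchangeable covariance. Adding an exchangeable error term leaves one parameter with nothing to identify it.

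Second, and more important, an exchangeable covariance assumes equal variance at every visit. The variance of a count rises with the expected number of events, and visits at unequal spacing need not have equal expected counts. The fitted model then applies one pooled variance to all visits. The standard error is too small where events are many and too large where they are few.

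At stake are the visit-specific treatment effects: the immediate benefit that E2.2 calls its main hypothesis, and the maintenance of gains. The primary test may also be exposed. With arm-by-time dummies in the model, the coefficient of treatment is the effect at the reference visit and not an average over visits.

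**Working it through.** **The plan's own figure.** No figure is given for the covariance model. The nearest is the minimum detectable difference in E2.2.1: sqrt(16/65) = 0.496, which rounds to the stated 0.50. It reproduces, and it shows that the primary model was planned on a linear, standardized-mean scale.

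**Redundancy.** Let b be the random-intercept variance, s the error variance and rho the error correlation. The marginal variance is b + s and the marginal covariance is b + rho·s, so three parameters determine two quantities. For (b, s, rho), the sets (0.4, 0.6, 0), (0, 1, 0.4) and (0.2, 0.8, 0.25) all give variance 1 and covariance 0.4. The marginal model, and hence each standard error, is the same as with either term alone.

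**Equal variance.** Take complete data, n = 65 per arm and a separate mean for each arm and visit. For visit t with true variance v_t, and mean variance v̄ over the three visits:

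- model SE² = 2v̄/n and true SE² = 2v_t/n
- SE ratio (model/true) = sqrt(v̄/v_t)
- rejection with no effect = 2[1 − Φ(1.96 × ratio)]

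**Assumed inputs.** The documents give no event rate, dispersion or counting window. I assume gamma-Poisson counts with dispersion 2 (variance m + 2m² for mean m) and 0.5 to 1 event per person-year.

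**Worked case: 1 event a year, constant rate, counted since the last visit.** The means are 0.25, 0.25 and 0.5.

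- Variances: 0.25 + 2(0.0625) = 0.375 (twice) and 0.5 + 2(0.25) = 1.0; v̄ = 1.75/3 = 0.583.
- SE ratios: sqrt(0.583/0.375) = 1.247 at 3 and 6 months; sqrt(0.583/1.0) = 0.764 at 12 months.
- Rejection: 1.5% at 3 and 6 months; 13.4% at 12 months.
- 12-versus-3-month interaction: the covariances 2·m_i·m_j are 0.125, 0.25 and 0.25, mean 0.208. Up to the factor 2/n, the model variance is 2(0.583 − 0.208) = 0.75 and the true variance is 0.375 + 1.0 − 2(0.25) = 0.875. The ratio is sqrt(0.75/0.875) = 0.926, and rejection is 7.0%.
- Average over visits: model (0.583 + 2 × 0.208)/3 = 0.333; true 3.0/9 = 0.333. There is no error.

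**Other patterns** (rejection at nominal 5%; first figure 0.5, second 1 event a year):

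| Pattern | 3 mo | 6 mo | 12 mo | 12 v 3 interaction |
|---|---|---|---|---|
| Since last visit, constant rate | 1.8, 1.5% | 1.8, 1.5% | 12.5, 13.4% | 6.7, 7.0% |
| Cumulative, constant rate | under 0.1% | 2.2, 1.8% | 16.1, 17.2% | 12.8, 13.6% |
| Front-loaded 2:1:1 | 12.5, 13.4% | 1.8, 1.5% | 1.8, 1.5% | 6.7, 7.0% |
| Equal events per window | 5% | 5% | 5% | 5% |

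Without overdispersion, the first row (variances 1:1:2) still gives about 11% at 12 months and 2% at 3 months.

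**Simulation.** With 20,000 trials per cell and the same closed-form standard errors, rejection in the first row was 13.0 and 13.4% at 12 months, 2.0 and 1.7% at 3 months, and 7.1 and 6.7% for the interaction. The average over visits rejected 4.9-5.3% in all patterns. Visit-specific variances brought each visit back to 4.6-5.2%. A smaller check that fitted the random-intercept model by REML (400 trials, 1 event a year, first pattern) gave 0.8, 2.0 and 15.5% at 3, 6 and 12 months. Its Monte Carlo standard error at 12 months is about 1.8 points, so it agrees.

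**The case against.** The strongest case against has four parts.

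*The windows and the constant rate are assumed.* This stands. A reader might infer that the 12-month test is bound to be too liberal and the 3-month test too conservative. The documents do not support a fixed direction. Section B2 puts the highest risk in the first month after discharge, and enrollment follows a crisis within 2 weeks, so a front-loaded pattern is plausible and reverses the error. Equal events per window remove it. Nothing in the plan secures that case, however.

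*The duplicate terms do no harm to inference.* This also stands. A reader might take the doubling as the cause of wrong standard errors. It costs identifiability and perhaps convergence, no more. The sentence may even be meant to describe one structure in two ways.

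*The large figures are for the effect at a visit, while E2.2 names interactions for maintenance.* Correct: with counts since the last visit the 12-versus-3-month interaction rejects 6-7%, not 12-14%. E2.2 also names baseline as the time reference while using baseline as a covariate, so the exact contrast is unsettled. A model with baseline among the outcomes is not covered by these calculations.

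*A count model may be intended.* E2.3 links the primary analysis to a generalized linear mixed model, and E1.1 allows transformation to normality. Under a log-link count model, variance follows the mean and is not forced equal. The linear reading is likelier: E2.2 speaks of an ANCOVA-type model with an error covariance, E2.2.1 bases power on a standardized mean difference, and negative binomial regression is named only for hospitalizations and crisis visits. It is not certain.

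**Conclusion.** The point holds in a limited form. On the linear reading, E2.2 specifies an over-parameterised covariance whose marginal form is compound symmetry, and it offers no heterogeneous variance, exposure offset or robust standard error for the primary model. Bootstrap intervals appear only for the exploratory analyses (E2.4.1). Whenever expected events differ between visits, the standard errors of visit-specific effects are wrong.

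Under the assumed rates and dispersion, a nominal 5% test of a visit effect can reject anywhere from under 0.1% to about 17%. Which visit is too liberal depends on the unstated counting window and on when events occur. The average over visits is unaffected. The primary test is safe only if it is that average, and the model as written does not make it so.

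A reader might extend this to WHODAS and ideation severity because E2.3 uses the same model. These are scale scores, and the argument from counting windows does not carry over. This is a cheap improvement to make and not a flaw that invalidates the trial.

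**What to change.** In section E2.2:

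- State the C-SSRS counting window at each visit and the error distribution of the primary model.
- If the model is linear, drop the redundant term and fit an unstructured covariance over the 3, 6 and 12-month visits with Kenward-Roger degrees of freedom. This takes 6 covariance parameters with 130 people.
- If counts are modelled with a log link, keep one random intercept, add a log-exposure offset for the length of the counting window, and use robust standard errors.
- Say which contrast the main effect stands for: the effect at a named visit or the average over visits.

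For WHODAS and ideation severity, an unstructured covariance is a sensible default and not a correction of this error.

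The cost is a few sentences of analysis plan and a negligible loss of degrees of freedom. Sample size and data collection do not change.

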D5.2 EHR variable construction: EHR measures are listed in Table 5. Monthly EHR sums will be averaged by quarter and by year. If categorical variables change over an aggregated time point, the most consistent designation over the analyzed epoch will be used.

Health Services Utilization
Outpatient Visits (any service)
Outpatient Visits (MH service)
Emergency or Urgent Care Visits
Inpatient MH
Inpatient (any service)
Pharmaceutical Utilization
Antidepressant
Antipsychotic
Mood Stabilizer
Anxiolytics
Other medications (non-psychiatric)
Change in Pharmaceutical
Antidepressant
Antipsychotic
Mood Stabilizer
Anxiolytics
Other medications (non-psychiatric)
Mental Health (Current and Lifetime)
Depression
Bipolar disorder
Schizophrenia or schizoaffective disorder
Generalized Anxiety Disorder
Posttraumatic Stress Disorder
Specific Phobia
Panic Disorder
Social Phobia
Personality Disorder
ADHD
SUD
Gambling Disorder
Eating Disorders
Suicidality

Table 5. EHR data extracted at baseline and follow-

E. DATA ANALYSIS

E1. Design and Sample Size

This is a single-site, two-arm RCT with individual participant urn randomization. We propose to randomize 130 Veterans. Approximately 65 will be randomized to active TMS+BCBT and 65 participants will be randomized to sham TMS+BCBT. Recruitment for the intervention will cease once randomization goals are met (i.e. n= ~65 Veterans per condition). Additionally, we will be enrolling 60 Veterans, who will be matched on age (within 5 years), primary psychiatric diagnosis, and sex, for a total of 190 Veterans to be enrolled. A subsample of these veterans (120 in total; one group (n=30) with suicide ideation and another group (n=30) with suicide attempts; and controls (n=60) will be used in the analyses of brain-based biomarkers for suicidality. Veterans will be assessed at the study timepoints outlined in C3. Assessments.

E1.1 Overall Analytic Approach across Aims

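### No single coding of the E2.2 model makes the group main effect the test of TMS and the group-by-time interactions the test of maintained gains

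*Combined protocol and SAP*

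**What the plan says.** Section E2.2 describes an ANCOVA-type mixed model in which "the outcome composite measure at follow-up time points (e.g., 3, 6, 12 months) will be regressed on baseline value of the outcome", together with design factors, treatment and "dummy variables for time (baseline as reference) and interactions of treatment assignment and time dummies".

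Two sentences then give the terms their roles. For the treatment effect: "The main effect of TMS as adjunctive to BCBT will be tested with the main effect of group assignment to the joint intervention condition". For durability: "The time effect interactions of TMS assignment test hypotheses about the maintenance of gains at 3, 6 and 12 months". The section adds: "Our main hypothesis is that there is an immediate beneficial effect of TMS exposure".

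Sections E2.2 and E2.2.1 give no margin, decision rule or power for maintenance. Section E2.3 uses the same model for the WHODAS score and C-SSRS ideation severity, so those outcomes inherit whatever is decided here.

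**The concern.** What a group main effect and a group-by-time interaction estimate depends on which rows are outcomes and which time is the reference. E2.2 gives both: follow-up visits are the outcome rows, and baseline is the reference level for time. These do not fit together, and the roles assigned to the two terms need different resolutions of the conflict.

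The stake is the durability claim. Section B2 argues that prevention should cover the year after hospitalisation or crisis, which is the period that the 6- and 12-month visits observe. If the model is resolved in favour of the stated TMS test, the maintenance test becomes a test of change in effect. A significant result then shows that the effect changed, and a non-significant one is weak evidence that it did not. If the model is resolved the other way, the stated TMS test no longer tests TMS.

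**Working it through.** **Inputs.** 65 per arm (E1, E2.2.1). Effect 0.50 SD (E2.2.1). Correlation .2 is the plan's pre-post value; I assume that it also holds between visits, and show .5 and .7 as a range. Exchangeable correlation (E2.2). SD = 1 on a normal scale, as in E2.2.1. Two-sided 5%; the plan does not state sidedness.

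**The plan's own figure.** Lehr's formula gives sqrt(16/65) = 0.496, which rounds to the stated 0.50. A two-group comparison with 65 per arm and d = 0.5 has power .813, so this figure reproduces.

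**Can the model be fitted as written?** The fixed effects, leaving out the design factors, are an intercept, the baseline value, group, three time dummies (3, 6, 12 months) and three interactions: 9 columns. With follow-up rows only, the three time dummies add up to the intercept and the three interactions add up to group. The rank is therefore 9 − 2 = 7, and the model is not estimable. Adding a baseline outcome row restores rank 9. Someone must choose between two readings.

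**Reading A: follow-up rows only, baseline as covariate, 3 months as reference.** The group term is the 3-month effect, which matches the stated TMS test and the hypothesis of an immediate effect. Each interaction is the effect at a later visit minus the effect at 3 months, so it is zero under full persistence.

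- SE of the arm difference at one visit: sqrt(2/65) = .175.
- SE of the 12 v 3 month change in that difference: sqrt(4(1 − rho)/65).

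| rho | SE | Rejects if 0.5 fully kept | Power if half lost (0.25) | Power if all lost (0.5) | All lost, missed |
|---|---|---|---|---|---|
| .2 | .222 | .05 | .203 | .615 | 39% |
| .5 | .175 | .05 | .297 | .813 | 19% |
| .7 | .136 | .05 | .452 | .957 | 4% |

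A loss of half the effect is missed 80%, 70% and 55% of the time. With an assumed 20% dropout (65 × 0.8 = 52 per arm), power for complete loss falls to .522 (rho .2) and .722 (rho .5), so it is missed 48% and 28% of the time. Simulation at rho .2 with 65 per arm (4,000 runs per scenario) rejected .054, .203 and .607 of the time for fully kept, half lost and all lost.

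By comparison, the 12-month active minus sham difference itself has power .813 if 0.5 SD is retained, or .829 after baseline adjustment at r = .2 (residual SD sqrt(.96)).

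**Reading B: baseline is an outcome row and the time reference.** Each interaction is the arm difference at that visit minus the baseline difference, so it equals 0.5 under full persistence. Power at 12 months is .615, .813 and .957 at rho .2, .5 and .7. The group main effect is now the baseline difference, which randomisation makes zero in expectation. It rejects 5% of the time whatever TMS does.

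**Effect of the plan's final alpha.** The plan says: "We will retain a significance level of 0.049 for our primary hypothesis at project completion". At .049 the powers for complete loss are .612, .811 and .956, and the rejection rate under full persistence is .049. Nothing changes.

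**The case against.** The strongest reply is that E2.2 names baseline as the reference and lists interactions at three visits, 3 months included. With 3 months as reference there would be no 3-month interaction, so the maintenance sentence fits Reading B, where the interactions are close to the visit-specific contrasts one would want. This stands. A reader might infer that, as written, a lasting benefit cannot produce a positive maintenance test, or that this test has 5% power. The text does not support that without condition: under Reading B it has about 62% to 81% power at 12 months for rho .2 to .5. But Reading B removes the TMS test stated in the preceding sentence, so it moves the conflict rather than resolving it.

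A reader might also infer that the investigators will call gains maintained when the interaction is not significant. No section says so. What can be said is that the plan offers no other rule.

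Third, maintenance is subsidiary to the immediate effect, and durability is also addressed by the Cox model for time to first attempt over 12 months (E2.2) and the exploratory trajectory models (E2.4). That limits the importance. It does not settle what the primary model's terms mean.

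Finally, a visit-specific CI that excludes zero shows that some benefit is present, not that none was lost, and a fully retained 0.5 SD effect would fail that criterion about 17% to 19% of the time at 12 months. Both points are right, and the wording of the fix allows for them.

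**Conclusion.** The point holds in a conditional form. The two roles that E2.2 assigns cannot both be correct in one model. Under the reading that keeps the main effect as the TMS test, the interactions are zero when gains fully persist, and the 12 v 3 month interaction misses a complete loss of effect about 39%, 19% or 4% of the time at between-visit correlations of .2, .5 and .7. Under the other reading the interactions are usable as visit effects, but the main effect has about 5% power for TMS.

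The miss rates assume 65 per arm with complete data, 0.5 SD at 3 months, exchangeable correlation and a normal scale. The primary outcome is a summed count of suicidal events, so they are indicative only. The conflict between the two roles does not depend on any of these figures. It should be settled before the analysis; it is not a reason to doubt the trial design.

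**What to change.** Specify follow-up rows only as outcomes, with the baseline value as covariate and 3 months as the time reference. The group term is then the 3-month effect. Replace the maintenance sentence with:

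> The active minus sham difference is estimated at 3, 6 and 12 months from the model (group plus the relevant interaction), each with a 95% CI. A benefit is said to be present at 6 or 12 months only if that CI excludes 0 in favour of active TMS. The 6 v 3 and 12 v 3 month interactions are reported with CIs as the estimated change in effect; a non-significant interaction is not evidence that gains were maintained.

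If the investigators want to claim that gains were kept, rather than that benefit is present, they would also need a pre-specified margin for the tolerable loss. The documents give none.

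The cost is one replaced sentence and the changed reference level. The contrasts come from the planned model, no new data are needed, and the change carries over to the E2.3 outcomes that use the same model.
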